Typical growth patterns have been defined **for** classical autosomal dominant OI types. Many of these children are small to normal size at birth, but virtually all Types III and IV patients begin to plateau in length beginning about 12 months. This continues through about age 4 years for Type IV, when most of these children begin to grow at normal growth rates, but below the lowest percentiles of the standard growth chart curve. It is possible that Type IV children could have normal stature if the plateau phase were eliminated. Type III children tend to demonstrate only small growth gains. [3] The reasons for this plateau phase are unknown. The National Institute of Child Health and Development (NICHD) has produced data addressing growth deficiency in older OI children, but there have been no efforts to date focused on the plateau phase in early childhood. [4]

At a molecular level, autosomal dominant osteogenesis imperfecta is associated with defects in either of the two chains which comprise type I collagen. [5] Type I collagen is a heterotrimer, made up of two α 1 chains and one α 2 chain, which constitutes the most abundant protein in bone, skin, and tendon. Inadequate amounts or abnormal forms of type I collagen can account for the matrix abnormalities, osteoporosis and bone fragility of OI. [6] The role of skeletal matrix abnormalities in short stature is unclear. Possible roles include unresponsiveness of the target tissue to local and systemic growth factors or abnormal feedback of target tissue on the endocrine axis.

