The pre-treatment interval will be a one year time period during which children will be serving as their own baseline controls. The visit schedule will be every 3 months. Linear growth on each side of the body will be measured at each visit with 5 lengths using a supine length board. Other measurements at each visit will include weight, arm span, sitting height, upper and lower extremity segments, and head circumference. At 6 month intervals, radiographic assessments of spine, and lower extremities will be performed, as well as bone density of the lumbar spine. Radiographic assessments of bone age will be done annually.

Children enrolled in this protocol will be co-enrolled in protocol 97-CH-0064 and will undergo pulmonary testing and neurological imaging on the schedule for that protocol. For pulmonary function testing, the tests will be completed at Children's National Medical Center. Children too young to cooperate with the procedures of pulmonary function testing will not be sedated for these procedures. Additionally, neuroimaging studies of the head and neck, including CT and MRI scan, will commence when the child is able to cooperate without needing sedation. In our experience, children age 4-5 years are able to hold still for the CT scan, which takes approximately 5-10 minutes. If signs of Basilar Invagination (BI) are detected, the children progress to having MRI scans every year.

An iliac crest bone biopsy will be obtained at the beginning of the treatment year for growth hormone. This biopsy will be repeated at the end of the growth hormone treatment year. The biopsies will be obtained by [name] for analysis in [name] laboratory. The procedure will be performed under general anesthesia in the operating room at the NIH.

During the pre-treatment year, the following testing will be done for endocrine evaluation.

1.5cc

2.	Somatomedin Generation Test [14]	3.2 cc / draw (includes discard)
		2.0 cc added to Baseline and Day 5
		20.0 cc total

Our experience with this test in OI children shows that 89% demonstrate a peak response beginning at 48 hours after the initial injection. Therefore we plan to do the full 6 day test, but only draw blood at baseline (day 0) and days 2-5. To evaluate for the possibility of growth hormone resistance, we will measure GHBP and IGFBP-3 at baseline and day 5 of this test.

3.	IGF-I	3.0 cc
	IGFBP-3, GHBP	
	Bone Specific Alk Phos	6.0 cc
	Osteocalcin, Type I Collagen Peptide	4.0 cc
	TSH, FT ₄ , T ₄	4.0 cc

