	Glycosylated Hemoglobin	5.0 cc
	Total	22.0 cc
Thece	growth factors will be obtained at 6 more	ath intervals

These growth factors will be obtained at 6 month intervals.

4. 6 hour gro	wth hormone sampling	1.7 cc/drav	v (inc	. discard); 32.	3 cc total
---------------	----------------------	-------------	--------	-----------------	------------

or 12 hour growth hormone sampling [17] 1.7 cc/draw (inc. discard); 62.9 cc total

The 6 hr testing will be used for patients with a minimum weight of 6.5 kg through 12.6 kg. The 12-hour evaluation will be done for children 12.7 kg or greater.

This endocrine testing will be spread out over the 3-month visit schedule to remain within the NIH guidelines for safe amounts of blood withdrawal from children. Scheduled visits will be inpatient on the 1 Northwest Pediatric unit when overnight serial blood testing or a bone biopsy is scheduled. Other scheduled visits will be outpatient day hospital visits.

VISIT	Meas	XR	BA	BMD	Growth	SGT	Serial	CBC	Bone	Pulm/Neuro
					Factors		GH		Biopsy	
Baseline	Х	LE,	Х	Х	Х			Х		Per 97-CH-
		spine								0064
3 month	Х					Х				
6 month	Х	LE,		Х	Х		Х			
		spine								
9 month	Х									
12 month	Х	LE,	Х	Х	Х			Х	Х	
(baseline		spine								
part B)										

PART B GROWTH HORMONE TREATMENT

In this part of the protocol, OI children will be treated with synthetic growth hormone (Humatrope[®], generously donated by Eli Lilly and Company) for one year to identify responders. Responders will be identified as those children who are able to achieve and sustain a 50% increase in growth rate over their baseline. Responders will be treated an additional 2 years. After the third year of treatment, responders will be defined as those children who demonstrate a sustained increase of 30% or greater from baseline. Children who are responders at the 3 year mark will be treated with growth hormone through final adult height. Final adult height will be defined as epiphyseal-metaphyseal union of the distal femur and proximal tibia growth plates. We will attempt to follow all participants through final adult height.

The planned visit schedule is every 3 months starting at the baseline period and continuing through treatment completion.

Visit	Measures	XR	Bone Age	Growth	Bone	Bone	Pulm/Neuro
				Factors	Density	Biopsy	
PART B	Х	Х	Х	Х	Х	Х	Per 97-CH-
BASELINE (Rx							0064
year, also part A							
12 mo visit)							
3 MONTH	Х						
6 MONTH	Х	Х		Х	Х		
9 MONTH	Х						
12 MONTH	Х	Х	Х	Х	Х	Х	

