RESPONDERS 6	Х	Х		Х	Х		
MONTH							
12 MONTH	Х	Х	X	Х	Х		
TREATMENT	Х	Х	X	Х	Х		
END, 3 YEAR							
NON-							
RESPONDERS							
ADULT	X	X	X	Х	X		
STATURE							

Parameters which will be followed during the treatment year will be a continuation of those followed during the pre-treatment year, and are summarized in the following table:

All visits will be outpatient day hospital visits with the exception of those visits when a bone biopsy is scheduled.

MONITORING SUBJECTS, DOSAGE, AND CRITERIA FOR WITHDRAWAL OF SUBJECTS FROM THE STUDY

Treatment with Humatrope[®] will begin at the 12 month pretreatment visit/baseline treatment visit. The accompanying parent will learn how to reconstitute the drug and administer the subcutaneous injections. The dose will be 0.06 mg/kg/day for 6 days of the week. At the end of 12 months of treatment, those children who have responded with a

sustained 50% increase in growth rate will remain on Humatrope[®] injections for an additional 2 years. After the third year of treatment, responders will be defined as those children who demonstrate a sustained increase of 30% or greater above baseline. These responders will be treated through attainment of final adult height as defined above.

STRATIFICATION AND RANDOMIZATION

All patients entering this study will undergo the same protocol as described above. There will be no randomization.

HUMAN SUBJECTS PROTECTIONS

Children enrolled in this study will be limited to those with Sillence Types III and IV OI, as determined by clinical and genetic criteria. This disorder is autosomal dominant, and occurs with equal distribution in males and females. The disorder has been described in all races and has no ethnic preference. There are no exclusionary criteria related to race or gender for this protocol.

CRITERIA FOR PATIENT SELECTION

Patients will be recruited with the goal of including at least 10 each of individuals with clinical/biochemical criteria of types III and IV OI who are between 3 and 8 years of age.

1. Height: Individuals with type III OI have severe short stature by definition; individuals with type IV OI recruited to the study will have height less than the 3rd percentile for age. All individuals will be required to furnish growth records, especially height and head circumference, from at least the preceding two years.

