The primary outcome is the change in growth rate from untreated to treated status. For the first year, a 50% increase in growth rate is considered a positive response. We suppose that growth rate is approximately normally distributed. From random chance, we estimate that the probability of observing a 50% increase in growth without intervention is less than 0.2. Therefore, we would like to test the null hypothesis that the proportion of responders in the population is less than or equal to 0.2 against the alternative that the proportion exceeds 0.2. Using a normal approximation to the binomial and assuming the true action of GH is to result in a population with mean 50% more than the untreated mean, we have 91% power with the sample size of 20.

Other protocol parameters will be correlated with linear growth responders versus nonresponders, as well as being analyzed for the group as a whole. These correlations will be made for both 6 month and one-year treatment intervals throughout the study.

NATURE OF FINANCIAL COMPENSATION

No financial payments will be offered to patients or their families.

References

- Marini JC, C.E., Osteogenesis Imperfecta, in Management of Genetic Syndromes, A.J. Cassidy SB, Editor. 2001, Wiley-Liss: New York. p. 281-300.
- 2. Marini, J.C., Osteogenesis imperfecta: comprehensive management. Adv Pediatr, 1988. 35: p. 391-426.
- 3. Ernst, M. and E.R. Froesch, *Growth hormone dependent stimulation of osteoblast-like cells in serum-free cultures via local synthesis of insulin-like growth factor I.* Biochem Biophys Res Commun, 1988. **151**(1): p. 142-7.
- 4. Rauch, F., et al., *Static and dynamic bone histomorphometry in children with osteogenesis imperfecta.* Bone, 2000. **26**(6): p. 581-9.
- 5. Prockop, D.J. and K.I. Kivirikko, *Heritable diseases of collagen*. N Engl J Med, 1984. **311**(6): p. 376-86.
- Prockop, D.J., et al., *The biosynthesis of collagen and its disorders (first of two parts)*. N Engl J Med, 1979. **301**(1): p. 13-23.
- 7. Cohen, P., et al., Consensus statement on the diagnosis and treatment of children with idiopathic short stature: a summary of the Growth Hormone Research Society, the Lawson Wilkins Pediatric Endocrine Society, and the European Society for Paediatric Endocrinology Workshop. J Clin Endocrinol Metab, 2008. 93(11): p. 4210-7.
- 8. Rose, S.R. and G. Municchi, *Six-hour and four-hour nocturnal sampling for growth hormone*. J Pediatr Endocrinol Metab, 1999. **12**(2): p. 167-73.

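### The 50% and 30% responder rules make no allowance for age, so natural recovery from the plateau can count as response in type IV children whose baseline year began before about age 4

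*Protocol*

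**What the plan says.** Part A sets the comparator: "The pre-treatment interval will be a one year time period during which children will be serving as their own baseline controls". Part B calls a child a responder after one treatment year if growth rate is at least 50% above that baseline. For the later decision it says: "After the third year of treatment, responders will be defined as those children who demonstrate a sustained increase of 30% or greater from baseline". The section on monitoring, dosage and withdrawal repeats the rule almost word for word: "After the third year of treatment, responders will be defined as those children who demonstrate a sustained increase of 30% or greater above baseline". Year-3 responders stay on growth hormone until final adult height. There is no randomization. Two years of earlier growth records are required at selection, but neither rule uses them.

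On untreated growth in type IV, the Introduction describes a plateau that begins at about 12 months and adds: "This continues through about age 4 years for Type IV, when most of these children begin to grow at normal growth rates". The population is aged 3 through 15, and the recruitment goal under Criteria for Patient Selection is "at least 10 each of individuals with clinical/biochemical criteria of types III and IV OI who are between 3 and 8 years of age".

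Evaluation of Results makes change in growth rate the primary outcome and says of the year-1 rule: "From random chance, we estimate that the probability of observing a 50% increase in growth without intervention is less than 0.2". It then adds: "Other protocol parameters will be correlated with linear growth responders versus nonresponders, as well as being analyzed for the group as a whole". And: "These correlations will be made for both 6 month and one-year treatment intervals throughout the study". Objective 1 asks for the range and duration of growth responsiveness.

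**The concern.** A percentage rise over a child's own earlier year measures the drug effect only if the untreated rate would have stayed where it was. For one group the protocol itself says that it does not stay there. A type IV child who enters at 3 has the baseline year at 3 to 4, inside the plateau, and treatment years 1, 2 and 3 at 4 to 7, after it. The comparison spans the end of the plateau whether *sustained* is read as the third-year rate or as the average over three years. The year-1 rule spans it too, so passing the 50% rule does not screen the problem out before year 3.

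At stake is how individual responder labels are read, and through them the duration part of Objective 1 and the comparisons of responders with non-responders. Some of what is counted as lasting responsiveness could be growth that would have returned without treatment.

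**Working it through.** **The plan's own figure.** Inputs from Evaluation of Results: null proportion 0.2, sample size 20, and a treated mean 50% above the untreated mean. Under a normal distribution that mean gives a responder proportion of 0.5. One-sided alpha of 0.05 is assumed, because the protocol states none.

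- Cut-off: 0.2 + 1.645 × √(0.2 × 0.8 / 20) = 0.347
- Power: Φ((0.5 − 0.347) / √(0.5 × 0.5 / 20)) = 0.914

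The stated 91% is reproduced. The point below does not change it.

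**What the rules require of growth hormone.** Let g be the untreated growth rate at the time of assessment divided by the untreated rate in the baseline year. If growth hormone multiplies the concurrent untreated rate, the effect needed is 1.50/g − 1 at year 1 and 1.30/g − 1 at year 3. The protocol gives no growth velocities, so every g is an assumption. For type IV children leaving the plateau, the text supports only the direction, g above 1.

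| Assumed g | Effect needed, year 1 | Effect needed, year 3 |
|---|---|---|
| 1.0 | 50% | 30% |
| 1.1 | 36% | 18% |
| 1.2 | 25% | 8% |
| 1.3 | 15% | 0% |

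The thresholds equal the concurrent drug effect only at g = 1.

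**How many children.** Assume 10 type IV children with entry ages even over 3 to 8. One of those five years lies before age 4, so 10 × 1/5 = 2 of 20 children have a baseline year that begins in the plateau. If children pass year 1 at the earlier cohort's rate of 19 of 36, then 20 × 19/36 = 10.6 children go on to year 3, of whom 2 × 19/36 = 1.1 are affected.

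**Effect on the year-1 null proportion.** Take the chance of an untreated 50% rise at its stated bound of 0.2. A normal model then implies an SD of relative change of 0.5 / 0.8416 = 0.594. For a child whose untreated rate rises by d, the chance of passing with no drug effect is 1 − Φ((0.5 − d) / 0.594). With 2 such children among 20, the expected untreated proportion is (18 × 0.2 + 2 × p) / 20, where p is that chance.

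A child who enters partway between 3 and 4 spends only part of the baseline year in the plateau. With even entry over that year the mean overlap is one half, so about half the rise is the fairer value for d.

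| Assumed full rise | p, full rise | Proportion, full rise | p, half rise | Proportion, half rise |
|---|---|---|---|---|
| 10% | 0.250 | 0.205 | 0.224 | 0.202 |
| 20% | 0.307 | 0.211 | 0.250 | 0.205 |
| 30% | 0.368 | 0.217 | 0.278 | 0.208 |

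Against a null of 0.20, the realistic shift is to about 0.202 to 0.208.

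**The case against.** The protocol nowhere calls 30% a continuing growth hormone effect. In the monitoring section the rule decides who stays on drug, and for that purpose a raw percentage is workable. This stands, and it is why the rule should be kept.

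Nor does the protocol say that duration will be read from the year-3 label alone. The primary outcome is the change in growth rate, other parameters are also analysed for the whole group, and lengths are taken every three months. A reader might infer that Objective 1 rests on the 30% label. The documents do not say so, and the harm arises only if the label is used that way.

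The numbers are small and every g is assumed. Eligibility runs to age 15 and the earlier treated cohort was aged 5 to 12, so the share of plateau children could be lower than 2 in 20. This also stands, and it limits the weight of the point.

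A reader might take the missing definition of *sustained* as a further error. It is operational detail that an analysis plan may supply, and either reading carries the same natural rise.

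What the objection does not remove is that the protocol itself fixes both rules, describes an untreated rise in growth rate in type IV, and admits children young enough for their baseline year to fall before that rise.

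**Conclusion.** The point holds in a limited form. For type IV children whose baseline year began before about age 4, both responder rules can credit natural recovery to growth hormone. The direction rests on the Introduction's account of untreated growth. The size cannot be computed from the protocol. On an even spread of entry ages over 3 to 8, about 2 of 20 children are affected at year 1 and about 1 of 10 to 11 at year 3.

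Two stronger readings are tempting and are not supported. One is that the primary test is compromised: the 91% power reproduces, and the expected untreated proportion moves only from 0.20 to about 0.202 to 0.208 under the assumptions shown. The other is that the rules mislead for the whole trial population. For type III the protocol reports only small growth gains, and for type IV children past the plateau it describes no further change in growth rate, so nothing can be claimed for either group.

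This is a minor point and a cheap improvement.

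**What to change.** Leave the treatment-continuation rule as it is. Add that the year-1 and year-3 responder summaries, and the statement on duration for Objective 1, will be repeated without type IV children whose baseline year began before about age 4, and that the report will say whether the conclusion changes.

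As a secondary descriptive result, report the change in growth-rate score for age and sex from the baseline year to treatment years 1, 2 and 3. Note beside it that reference rates from children without OI do not remove the rise on leaving the plateau. The score therefore supplements the repeated summaries and cannot replace them.

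The data needed (lengths, OI type and age at entry) are already part of the study. The cost is about 1 to 2 fewer children in a descriptive summary and a little more analysis work. No formal subgroup test is needed.

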The maximum blood volume required for the endocrine evaluation when all testing is done in one visit is 76 cc, which can safely be obtained from a 15.2 kg child. We expect to do this testing in 2 separate visits, 6 months apart so as not to exceed the safe blood limit parameters defined by Clinical Center policy. NIH policy limits the volume of blood drawn from children to 9.5 milliliters per kilogram of body weight in any 8-week period of time and 5 milliliters per kilogram of body weight at any one time.

Iliac Crest Bone Biopsy: Bone biopsies are now performed in the operating room at the NIH with patients under general anesthesia. Anesthesiologists from the Department of Anesthesia and Surgical Services at the NIH clinical center manage general anesthesia and closely monitor risks associated with general anesthesia such as suppression of respiratory and cardiac function. With appropriate sedation, an iliac crest biopsy is a relatively simple procedure. Plugging of the biopsy site with Surgicel or gel foam, together with placement of a compressive dressing, prevents bleeding and also encourages rapid clot organization. Two small stitches will be used to close the skin wound. In our experience, the short course of tetracycline administration has never provoked tooth staining. The drug should be administered after meals and long duration exposure to sunlight prevented during those days. Rarely, the drug causes skin hypersensitivity to sunlight that may induce first degree sunburn. Discomfort in the hours following the biopsy is easily controlled with pain relievers such as Tylenol or Tylenol with codeine.

Humatrope[®] injections: Parents will be taught to administer subcutaneous injections of Humatrope[®]. They will use an insulin syringe and needle for this daily procedure. There is no discomfort connected with the delivery of the hormone itself. The discomfort will consist of the insertion of a very small needle under the skin and should be minimal.

ADVERSE EVENTS

All serious, unexpected adverse events (those not included in the investigators brochure), related to the use of Humatrope[®] will be reported to Eli Lilly and Company. Unexpected, serious adverse events will be reported to the FDA as well, within 15 days of the event, and within 7 days in the case of a death or life-threatening event. The known risks of

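### The stated 76 cc maximum blood draw leaves out the 12-hour test (true maximum 106.4 cc), and the scheduled 6-month visit exceeds the protocol's own 5 mL/kg limit in part of both weight bands

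*Protocol*

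**What the plan says.** Hazards and Discomforts (endocrine evaluation for Parts A and B) states: "The maximum blood volume required for the endocrine evaluation when all testing is done in one visit is 76 cc". It adds that a child of 15.2 kg can safely give this amount. The same paragraph cites the NIH limits: 9.5 mL/kg over 8 weeks and "5 milliliters per kilogram of body weight at any one time". On scheduling it says: "We expect to do this testing in 2 separate visits, 6 months apart".

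Part A itemises the volumes and assigns the serial growth hormone (GH) test by weight:

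- "The 6 hr testing will be used for patients with a minimum weight of 6.5 kg through 12.6 kg", at 32.3 cc in total.
- "The 12-hour evaluation will be done for children 12.7 kg or greater", listed as "1.7 cc/draw (inc. discard); 62.9 cc total".

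Of the growth factor panel (22.0 cc) it says: "These growth factors will be obtained at 6 month intervals". The Part A visit table marks growth factors at baseline, 6 and 12 months, the somatomedin generation test at 3 months, and serial GH at 6 months. Part A also says that testing is spread over the 3-monthly visits to keep within the NIH guidelines.

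**The concern.** A figure presented as the maximum should use the larger of the two serial tests. The 15.2 kg example child is above the 12.7 kg cut-off and so gets the 12-hour test, which the 76 cc does not appear to include.

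The weight bands raise a second question. If they were set from the serial sampling alone, they leave no room for another draw at the same visit, yet the table puts the growth factor panel on the same 6-month row. Staff who apply the bands and the table as printed could then exceed a paediatric blood limit that the protocol itself cites. The schedule is not optional for families either: under Off Study Criteria, failure to comply with blood draws or visits is a ground for withdrawal.

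**Working it through.** **Inputs (Protocol, Part A, except the limits, which are in Hazards and Discomforts)**

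- Item 1: 1.5 cc. Its label is not legible in the text at hand; it is assumed to be the blood count.
- Somatomedin generation test: the plan is to "only draw blood at baseline (day 0) and days 2-5", which is 5 draws of 3.2 cc, plus 2.0 cc on two of those days. 5 × 3.2 + 2 × 2.0 = 20.0 cc, as printed.
- Growth factor panel: 3 + 6 + 4 + 4 + 5 = 22.0 cc, as printed.
- 6-hour series, every 20 minutes: 6 × 3 + 1 = 19 draws; 19 × 1.7 = 32.3 cc, as printed.
- 12-hour series: 12 × 3 + 1 = 37 draws; 37 × 1.7 = 62.9 cc, as printed.
- Limits: 5 mL/kg at one time and 9.5 mL/kg in 8 weeks.

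**Step 1. Reproduce the plan's figure.** With the 6-hour series: 1.5 + 20.0 + 22.0 + 32.3 = 75.8, or about 76 cc; 76 / 5 = 15.2 kg. Both printed figures are recovered. No other combination of the five components comes within 1.6 cc of 76.

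**Step 2. The maximum with the 12-hour series.** 1.5 + 20.0 + 22.0 + 62.9 = 106.4 cc.

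- Weight needed: 106.4 / 5 = 21.3 kg.
- At 15.2 kg: 106.4 / 15.2 = 7.0 mL/kg.
- Without the unlabelled item: 104.9 cc and 21.0 kg.

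The 76 cc total cannot be given within the limit to any child who actually gets the 6-hour test. At the top of that band, 75.8 / 12.6 = 6.0 mL/kg.

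**Step 3. Where the weight bands come from.** 32.3 / 5 = 6.46 kg and 62.9 / 5 = 12.58 kg. These match the 6.5 and 12.7 kg cut-offs, so the bands appear to cover the serial sampling and nothing else.

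**Step 4. The scheduled 6-month visit (panel plus serial GH).**

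| Serial test | Visit total | Weight needed at 5 mL/kg | At lowest weight in band | Part of band over the limit |
|---|---|---|---|---|
| 6-hour | 22.0 + 32.3 = 54.3 cc | 10.86 kg | 54.3 / 6.5 = 8.4 mL/kg | 6.5 to 10.8 kg |
| 12-hour | 22.0 + 62.9 = 84.9 cc | 16.98 kg | 84.9 / 12.7 = 6.7 mL/kg | 12.7 to 16.9 kg |

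**Step 5. The 8-week limit.** 54.3 / 9.5 = 5.7 kg and 84.9 / 9.5 = 8.9 kg. Both are below the lower edge of the corresponding band, so this visit does not exceed the 9.5 mL/kg limit.

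**Step 6. Text against table.** The hazards text puts the testing in two visits six months apart. The table puts the somatomedin test and the serial sampling three months apart, with panels at baseline, 6 and 12 months.

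**The case against.** The case for leaving the text alone has four parts.

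- **The 76 cc case is hypothetical.** The protocol plans to split the testing, and no scheduled visit draws 76 or 106.4 cc. This is right: the 7.0 mL/kg figure is not a scheduled exposure. The sentence is still wrong as a statement of the maximum and of the weight at which it is safe.
- **A general instruction governs.** Part A says the testing is spread out to stay within NIH guidelines, so careful staff would split the 6-month draws. They might. But the Part A table is how the protocol does that spreading, and it still places both draws on one visit. A general intention does not correct a specific schedule that conflicts with it.
- **One time is not defined.** If the panel and the overnight series were drawn on different days and counted separately, the 6-month excess would weaken. That is a real assumption. However, the protocol divides a whole-visit total by 5 to get 15.2 kg, and that total includes the multi-day somatomedin test. Treating a visit as one occasion is therefore its own convention, and nothing separates the two draws at month 6.
- **The number of children affected is unknown.** The protocol gives no weight distribution, and nothing shows that any participant is near 6.5 kg. This stands. It limits what can be said about frequency, but the bands expressly provide for these weights.

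The mismatch over two visits six months apart is minor. Three months is already longer than the 8-week window, so that mismatch by itself breaches no limit.

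**Conclusion.** The concern holds. The stated maximum is the 6-hour total; the true all-in-one maximum is 106.4 cc, which is 30.4 cc above the printed 76 cc and needs 21.3 kg rather than 15.2 kg. As tabled, the 6-month visit exceeds 5 mL/kg from 6.5 to below 10.86 kg (up to 8.4 mL/kg) and from 12.7 to below 16.98 kg (up to 6.7 mL/kg). Children from 10.9 to 12.6 kg, and from 17.0 kg upward, are within it.

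The first result is arithmetic on printed figures and does not depend on the unlabelled 1.5 cc item. The second assumes that draws at one visit count as one occasion, in line with the protocol's own calculation. Only the single-occasion limit is affected. No endpoint or analysis is touched, but a paediatric safety figure is wrong as written and should be corrected.

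**What to change.** 1. In Hazards and Discomforts, give the all-in-one maximum as 106.4 cc (21.3 kg at 5 mL/kg) with the 12-hour test, and label 76 cc as the 6-hour total.
2. Make the 6-month visit meet 5 mL/kg on its whole volume, in one of two ways:
   - Move the serial GH sampling to the 9-month visit, which has no blood tests in the Part A table. The existing bands then work: 32.3 / 6.5 = 4.97 and 62.9 / 12.7 = 4.95 mL/kg. The panel keeps its 6-month interval.
   - Keep both draws at 6 months and reset the bands to 10.9 to 16.9 kg for the 6-hour test and 17.0 kg or more for the 12-hour test. Say what is done below 10.9 kg.
3. State whether draws within one visit count as one occasion.
4. Align the sentence about two visits six months apart with the table.

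The cost is a wording and table correction. Under the first option the inpatient stay for serial sampling moves from month 6 to month 9. Under the second, some lighter children get the 6-hour instead of the 12-hour series. Neither adds patients or procedures.
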